## 5.12 COMPLIANCE & ADHERENCE

Suitable participant information and fully informed consent procedures will ensure that participants understand the study requirements.

The study vaccines will be given in hospital by clinic nurses intramuscularly therefore few problems with compliance or adherence are envisaged. Compliance and adherence to the cART and vorinostat treatment regimens will be assessed at clinic visits through interview with the participant. Participants will be interviewed about missed doses at study visits, and if they do occur these will be recorded in the CRF.

## 5.13 TREATMENT DATA COLLECTION

Every drug prescribed, its dose, frequency, route of administration, and duration will be recorded in the study case report forms (CRF).

## 5.14 CONCOMITANT MEDICATIONS

### 5.14.1 MEDICATIONS PERMITTED

Antibiotics to treat intercurrent infection, treatment for other co-morbidities not contraindicated for the study e.g. diabetic treatment, hypertension treatment, lipid lowering agents and inhaled corticosteroids are all permitted for concomitant use.

### 5.14.2 MEDICATIONS NOT PERMITTED

The following medications are not permitted for concomitant use:

- Immunosuppressive drugs (inhaled corticosteroids are permitted).
- Chemotherapy drugs.
- Other HIV vaccines.
- All medication whose co-administration with ritonavir boosted protease inhibitor (e.g. darunavir), raltegravir and NRTI backbone (e.g. Truvada® or Kivexa®) is contraindicated. See details in the relevant SmPC.
- In Arm B drugs that have been associated with Torsades de Pointes and/or are associated with QT shortening (see [Appendix I](#) and reference [www.torsades.org](http://www.torsades.org)).
- In Arm B, other HDACi i.e. sodium valproate.

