#### 1.1.1.B PHARMACOKINETIC/PHARMACODYNAMIC – EFFECTS ON QTc

The “normal” range for QTc interval from the general population, as measured by 12-lead ECG, is generally considered to be between 350 and 440ms. In addition the actual clinical relationship between drug-induced QTc interval prolongation and Torsades de Pointes is likely only with very long intervals (> 500ms) and is less defined with smaller interval changes. The Division of AIDS toxicity grading table (see [Appendix III](#)) defines abnormal QTc interval as:

- Grade 1 - 0.45 – 0.47 sec OR increase interval < 0.03 sec above baseline
- Grade 2 - 0.48 – 0.49 sec OR increase in interval 0.03 - 0.05 sec above baseline
- Grade 3 -  $\geq 0.50$  sec OR increase in interval  $\geq 0.06$ sec above baseline
- Grade 4 - Life threatening consequences e.g. Torsade de pointes or other associated ventricular dysrhythmia.

Data on vorinostat and QTc prolongation is largely derived from patients taking this drug for the treatment of cutaneous T cell lymphoma (CTCL). In 25 healthy volunteers given a single supratherapeutic dose of vorinostat 800mg, no patient had a significant change in QTc over 24 hours of ECG monitoring. In other studies 3 of 86 (3.4%) CTCL patients exposed to 400mg QD had Grade 1-2 QTc prolongation. In a retrospective analysis of 5 studies (3 Phase I trials and 2 Phase II trials), 4 of 116 (3.4%) evaluable patients had grade 2 QTc prolongation, and 1/116 (0.8%) had grade 3 QTc prolongation. Of 49 non-CTCL patients from 3 clinical trials, 1 had grade 2 prolongation and 2 had grade 3 QTc prolongation.

The first study to use multiple doses of vorinostat in HIV-positive individuals excluded individuals from enrolment with a QTc value >450msec. In the Lewin study, vorinostat was administered as 14 continuous 400mg daily oral doses. There were no Serious AEs related to QTc prolongation in this study.

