### 3.3.2 ENROLMENT EXCLUSION CRITERIA

1. Women of child bearing potential (WCBP)§
2. In women with intact ovaries and no uterus, any planned egg donation anytime in the future to a surrogate
3. Intention to donate sperm or father a child within 6 months of the intervention
4. Co-infection with hepatitis B (surface antigen positive or detectable HBV DNA levels in blood) or hepatitis C (HCV RNA positive or HCV antigen positive)
5. Any current or past history of malignancy
6. Concurrent opportunistic infection or other comorbidity or comorbidity likely to occur during the trial e.g. past history of ischaemic or other significant heart disease, malabsorption syndromes, autoimmune disease
7. Any contraindication to receipt of BHIVA recommended combination antiretrovirals
8. HIV-2 infection
9. Known HTLV-1 co-infection
10. Prior immunisation with any experimental HIV Immunogens (including any component of the vaccines used in the RIVER protocol; simian or human adenoviral vaccine; other experimental HIV vaccines)
11. Current or planned systemic immunosuppressive therapy (inhaled corticosteroids are allowed)
12. Any history of proven thromboembolism (pulmonary embolism or deep vein thrombosis)

---

† using current cut-offs for optical density as defined by PHE

‡ females aged <20 years of age, and weighing <65kg and <168cm in height will need to have an estimation of blood volume (EBV) >3500mL prior to enrolment. This circumstance is unlikely to arise as most women between the ages of 18 to 20 years would be of child-bearing potential (CBP) and excluded on that basis.

§ defined as any female who has experienced menarche and who has not undergone successful surgical sterilisation (hysterectomy or bilateral oophorectomy) or is not postmenopausal (defined as amenorrhoea  $\geq$  12 consecutive months; or women on hormone replacement therapy (HRT) with documented serum follicle stimulating hormone (FSH) level > 35mIU/mL); NB bilateral tubal ligation is reversible, a women with only tubal ligation who does not meet any of the other criteria is considered a WCBP

13. Any inherited or acquired bleeding diathesis including gastric or duodenal ulcers, varices
14. Concurrent or planned use of any drugs contraindicated with vorinostat i.e. antiarrhythmics; any other drugs that prolong QTc; warfarin, aspirin, sodium valproate
15. Prior intolerance of any of either the components of the vaccine or HDACi,

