16. Uncontrolled diabetes mellitus defined as an HBA1C>7%
17. Any congenital or acquired prolongation of the QTc interval, with normal defined as  $\leq 0.44s$  ( $\leq 440ms$ )
18. Participation in any other clinical trial of an experimental agent or any non-interventional study where additional blood draws are required; participation in an observational study is permitted
19. Allergy to egg
20. History of anaphylaxis or severe adverse reaction to vaccines
21. Planned receipt of vaccines within 2 weeks of the first trial vaccination administered at PR week 00 (including vaccines such as yellow fever; hepatitis B, influenza)
22. Abnormal blood test results at screening including
  - a. Moderate to severe hepatic impairment as defined by Child-Pugh classification
  - b. ALT >5xULN
  - c. Platelets <150x10^9/L
  - d. eGFR <60\*\*
  - e. uPCR >30 mg/mmol
23. Physical and laboratory test findings: Evidence of organ dysfunction or any clinically significant deviation from normal in physical examination and/or vital signs that the investigator believes is a preclusion from enrolment into the study
24. Active alcohol or substance use that, in the Investigator's opinion, will prevent adequate adherence with study requirements
25. Insufficient venous access that will allow scheduled blood draws as per protocol

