## 5.5 CRITERIA FOR STARTING VORINOSTAT

Safety assessments will be undertaken to ensure it is safe for participants randomised to Arm B to receive vorinostat at post-randomisation week 08 day 3 (PR08-3). Only participants who meet these criteria will proceed to receive dosing with vorinostat.

Arm B participants must meet the following criteria at post-randomisation week 08 day 1 (PR08-1) in order to commence vorinostat 2 days later at post-randomisation week 08 day 3 (PR08-3):

1. Participant is willing to continue on combination antiretroviral therapy
2. Platelet count  $\geq 150 \times 10^9/L$
3. eGFR  $\geq 60^{**}$
4. Adequate haemoglobin (Hb  $\geq 12g/dL$  for males,  $\geq 11g/dL$  for females)
5. ALT  $< 5 \times ULN$
6. QTc interval normal, with normal defined as  $\leq 0.44s$  ( $\leq 440ms$ )

Any out-of-range results from the above indicate that the participant must not receive vorinostat. Participants in Arm B will then be followed for the rest of the study as per study visit schedule. Analysis of their data will be included as part of the intention to treat analysis of the primary study end point (see [Section 9.5](#))

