#### 5.8.1.A SPECIFIC GUIDELINES FOR MANAGEMENT OF EXPECTED TOXICITIES:

- **Diarrhoea** – management with loperamide is strongly encouraged.
- **Dehydration** – encourage anti-emetics and anti-diarrhoeals as appropriate; encourage drinking of at least 2L fluid per day. Rehydration solutions are also encouraged as appropriate.
- **Nausea and vomiting** – aggressive management is encouraged.
- **Hyperglycaemia** – monitor blood glucose closely, treat with hypoglycaemic agents as appropriate.
- **Electrolyte disturbance** – replace potassium, calcium and magnesium as appropriate, as guided by regular blood electrolyte tests.
- **Venous thromboembolism** – monitor closely for signs and symptoms and investigate if there is suspicion of embolic event or venous thrombosis
- **QTc prolongation** – aggressively manage electrolyte disturbances.
- **Hematologic toxicities:**
  - **Anaemia** – transfuse as per institutional guidelines. Erythropoietin is allowed on-study as per prescribing guidelines.
  - **Neutropenia** – G-CSF is allowed on-study at investigator discretion.
  - **Thrombocytopenia** - Platelet transfusions should be administered in the following situations:
    - Platelets  $<10 \times 10^9/L$ .
    - Platelets  $<20 \times 10^9/L$  with fever  $\geq 38.5^\circ C$  due to infection or presumed infection (at discretion of treating clinician).
    - Platelets  $<20 \times 10^9/L$  with clinically significant bleeding (at discretion of treating clinician).
    - Platelets  $<50 \times 10^9/L$  in participants having invasive procedures (at discretion of treating clinician).

If the participant is intolerant of the 300mg every third day dose, then the drug should be ceased all together, see [Section 5.7](#).

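### Section 5.14.2 bars QT-shortening drugs in Arm B where the rest of the plan guards against prolongation, so it does not expressly bar a newly started QTc-prolonging drug that has no Torsades association

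*Protocol*

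**What the plan says.** Protocol Section 5.14.2 gives the drugs that may not be taken during the study. For QT effects, its entry reads "In Arm B drugs that have been associated with Torsades de Pointes and/or are associated with QT shortening", followed by a pointer to Appendix I and to a reference website on Torsades.

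The entry criteria are worded differently. Exclusion 14 for Cohort I (Section 3.3.2) rules out "Concurrent or planned use of any drugs contraindicated with vorinostat i.e. antiarrhythmics; any other drugs that prolong QTc; warfarin, aspirin, sodium valproate". Exclusion 13 for Cohort II (Section 3.4.2) uses the same words. Neither requires a Torsades association.

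The separate exclusion on the interval itself is "Any congenital or acquired prolongation of the QTc interval, with normal defined as" at or below 440 ms. Section 5.14.1 permits "treatment for other co-morbidities not contraindicated for the study", along with antibiotics and some other classes. Section 5.14.3, on drugs to be used with caution, deals with NSAIDs and antacids and does not mention QT effects.

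**The concern.** Section 5.14.2 is where a site would look when an Arm B participant needs a new drug after randomisation. Vorinostat exposure occurs only on study, so the on-study list ought to bar at least the QTc-prolonging drugs that the entry list calls contraindicated. As worded, its second limb names the opposite effect, one that the plan nowhere else treats as a risk.

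A new prescription during dosing is foreseeable. Section 5.8.1.A encourages anti-emetics and loperamide, and Section 5.14.1 allows antibiotics for intercurrent infection. The documents do not say whether any of these agents prolongs QTc, which is the question a prescriber would bring to Section 5.14.2.

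What is at stake is the clarity of a participant-safety rule. No estimate or test in the SAP depends on it.

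**Working it through.** **Step 1. Which direction does each QT provision address?**

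| Place | Content | Direction |
|---|---|---|
| Protocol 1.1.1.B, toxicity grades | Longer intervals or increases over baseline | Prolongation |
| Protocol 1.1.1.B, vorinostat data | Counts of patients with longer QTc | Prolongation |
| Protocol 3.3.2 (14) and 3.4.2 (13) | Drugs contraindicated with vorinostat | Prolongation |
| Protocol 3.3.2 (17) and 3.4.2 (16) | QTc exclusion, normal at or below 440 ms | Prolongation |
| Protocol 3.3.3 (5) | Cohort I randomisation, at or below 440 ms | Upper limit only |
| Protocol 5.5 (6) | Start of vorinostat, at or below 440 ms | Upper limit only |
| Protocol 5.8.1.A | Under QTc prolongation: "aggressively manage electrolyte disturbances" | Prolongation |
| SAP 4.9 | Number with QTc at or below 440 ms | Upper limit only |
| **Protocol 5.14.2** | **Drugs barred in Arm B** | **Torsades and/or shortening** |

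The only lower value is in Section 1.1.1.B, which says that the normal interval "from the general population, as measured by 12-lead ECG, is generally considered to be between 350 and 440ms". That describes a population; no criterion uses 350 ms. Section 5.14.2 is the only place where shortening appears as a concern.

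**Step 2. What does the literal rule leave out?** It has two limbs, Torsades-associated drugs and QT-shortening drugs. Three cases follow:

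- A QTc-prolonging drug with a Torsades association is barred by the first limb.
- A QTc-prolonging drug without that association falls under neither limb, although exclusions 14 and 13 call it contraindicated.
- If its use was already under way or planned at entry, the exclusions catch it. What remains is an unplanned drug started after randomisation.

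**Step 3. How long is the period not covered by the QTc check?** Section 5.5 requires "QTc interval normal, with normal defined as" at or below 440 ms at PR08-1; otherwise vorinostat must not be given. Visit codes are from Tables 3 and 4 and dosing is from Sections 5.4 and 5.6.4. Count each visit as 7 × week + day:

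- PR08-1 = 7 × 8 + 1 = 57
- PR08-3 (first dose) = 7 × 8 + 3 = 59
- PR10-1 = 7 × 10 + 1 = 71
- PR12-2 (last dose) = 7 × 12 + 2 = 86

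First to last dose is 86 − 59 = 27 days, or 28 days inclusive. At one dose every third day this gives 27/3 + 1 = 10 doses. Both figures match the protocol.

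From the PR08-1 check to the last dose is 86 − 57 = **29 days**. The schedule lets PR08-1 move by up to 2 days, so this is approximate.

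The PR10-1 ECG, recorded in Section 16 as added in version 4.0, falls 71 − 59 = 12 days after the first dose. That is dose 12/3 + 1 = 5, with 10 − 5 = 5 doses to come. It divides the 29 days into 14 before and 15 after.

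**Step 4. How many people does the rule apply to?** At 1:1 allocation, Arm B has 52/2 = 26 participants (the number assumed in Section 9.3) and at most 60/2 = 30. How many of them would start a QTc-prolonging drug without a Torsades association in those 29 days is not given and cannot be derived.

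**The case against.** The strongest reply is that the slip makes little practical difference. Each argument has some force.

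- **The Torsades limb does much of the work.** This stands. The literal gap is confined to prolonging drugs without that association. Section 1.1.1.B also says that the link between drug-induced prolongation and Torsades is likely only above 500 ms and is less defined for smaller changes.
- **Appendix I may list the drugs.** This stands as a possibility. The rule points to Appendix I, which was not available. If it names QTc-prolonging drugs, sites using it would be guided correctly, though it would then disagree with the body text.
- **The entry criteria and Section 5.14.1 already point to a bar.** This stands in part. A drug labelled contraindicated with vorinostat at entry would not readily be thought allowed later. But the exclusions are worded for concurrent or planned use, and a reader has to infer that they carry over.
- **The PR08-1 check is preventive.** This stands. Prolongation beyond 440 ms already present then blocks vorinostat, whatever drug caused it. The check tests the interval and not the drug list, so it cannot act on a drug started afterwards.
- **Later monitoring exists.** The PR10-1 ECG and the Table 5 rule to cease vorinostat at grade 3 or 4 non-haematological toxicity limit harm, but only after both drugs have been taken.

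A reader might infer that the protocol allows QTc-prolonging drugs generally in Arm B. The documents do not support that, for the first three reasons above. A reader might also take the whole time from randomisation to the last dose as the exposed period. That overstates it, because the PR08-1 check stands between any earlier prescription and vorinostat.

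**Conclusion.** The concern holds as a wording error in a live safety rule. Section 5.14.2 names the wrong direction of QT effect and, read literally, does not expressly bar a QTc-prolonging drug without a Torsades association that is newly started after randomisation. The period not covered by the PR08-1 check is about 29 days, in an arm of 26 to 30 participants.

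The practical gap is small, and its size in participants cannot be calculated from the documents. It is tempting to use the background figure that "4 of 116 (3.4%) evaluable patients had grade 2 QTc prolongation, and 1/116 (0.8%) had grade 3 QTc prolongation", which is 5/116 = 4.3% at grade 2 or 3. That rate describes vorinostat's own effect in earlier studies and would be the same whichever word Section 5.14.2 used, so it does not measure this error. The same section also reports no serious adverse events related to QTc prolongation with 14 daily 400 mg doses in HIV-positive participants; this trial doses every third day.

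A reader might also infer a second gap from the absence of antiarrhythmics, warfarin and aspirin by name in Section 5.14.2. The documents do not establish one: the entry criteria and Section 5.14.1 bear on those drugs, and Appendix I may list them. Barring them on study would be a new rule and not a correction of this word.

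Confidence is high that the word is wrong. Confidence in a working gap at sites is lower, because it depends on Appendix I. Sample size, power and the primary analysis are unaffected.

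**What to change.** In Protocol Section 5.14.2, change *QT shortening* to *QT prolongation* in the Arm B entry. Confirm that Appendix I agrees, and correct it if it does not.

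Optionally, while Appendix I is open, check whether the other drugs named in exclusions 14 and 13 are meant to stay barred during vorinostat dosing. That is a clinical decision and separate from this correction.

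The cost is one word and one check. No visit, test, CRF item or analysis changes. The edit needs a protocol amendment, which Section 11.2.2 sends to the ethics committee, so it is best carried with the next one; sites can be told of the intended reading in the meantime.

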### 5.14.3 MEDICATIONS TO BE USED WITH CAUTION

Intermittent use of non-steroidal anti-inflammatory drugs (NSAIDs), caution is only required if these are given within a week of or during receipt of vorinostat in Arm B participants. The reason for caution is that all NSAIDs can impair platelet function. One of the most common side-effects of vorinostat is thrombocytopenia, and this coupled with impaired platelet function might increase the risk of bleeding.

Co-administration of raltegravir with aluminium and magnesium antacids results in reduced raltegravir plasma levels, separate doses by at least 2hrs to avoid chelation effects on raltegravir and reduced absorption. More information is also provided in [Appendix I](#).

## 6 ASSESSMENTS & FOLLOW-UP

All randomised participants will be asked to attend follow-up visits until week 18 after randomisation (PR18) in order to assess primary outcome measures. Participants will also be invited to an annual follow-up visit at the site for 5 years following the end of the interventional part of the study.

Staff recording clinical data will be identified by each site Principal Investigator, receive appropriate training and sign a delegation Log. Clinical data will be obtained through consultation with the participant, their medical team, or their medical records. Laboratory measures will be extracted from participant notes/electronic records; study nurses will administer the QOL questionnaires to participants. All data will be recorded on paper CRFs submitted to the RIVER Co-ordinating Centre for processing within 7 days of the study visit.

Any additional visits or diagnostic/laboratory tests needed for participant management should occur as required at the discretion of the treating physician.

### 6.1 TRIAL ASSESSMENT SCHEDULE

Procedures planned at study visits follow the schedules outlined in **Table 1** (Cohort I - Previously diagnosed) and **Table 2** (Cohort II - Recently diagnosed). Participants will be provided with a summary of what to expect at study visits prior to providing consent, to ensure they are fully informed of the commitment required as part of the RIVER study. Details of logistics surrounding study visits will be included in study specific working practices and training for study staff will be provided.

#### 6.1.1 SCREENING

For Cohort I – Recently diagnosed, one of the eligibility criteria for enrolment in to the RIVER study is a confirmed HIV diagnosis within 4 weeks of enrolment. Therefore, potentially eligible individuals must undergo all tests required for assessment of eligibility in the 4 weeks following diagnosis. All results from this screening must be available for enrolment (Week 0).

For Cohort II – Previously diagnosed, group potentially eligible individuals must undergo all tests required for assessment of eligibility in the 2 weeks prior to randomisation. All results from this screening must be available for randomisation.

All participants must be given adequate information about the study together with a Participant Information Leaflet (**Appendix VII**) and be given an opportunity to ask questions about the study. There will be separate Participant Information Leaflets for each cohort. Study staff will be asked to maintain a log of participants who are not eligible or do not agree to take part in the study.

Study staff will ascertain that the information leaflet has been fully understood and obtain written informed consent before any study procedures are carried out. All individuals screened must have their name, date of birth and study number recorded in the Trial Register and have appropriate CRFs completed. The register must be stored by the investigator in a secure place only accessible to appropriate clinical staff. If an individual is not subsequently randomised the reason should be recorded in the register.

There will be a clinic interview, during which baseline demographics, clinical and behavioural data relevant to the eligibility criteria in [Section 3.3](#) and [Section 3.4](#) will be collected onto a CRF.

Screening will include:

1. Recording the clinical history, including HIV test results (Resistance test), Hepatitis B (sAg, sAb, Core Ab) Hepatitis C serology (HCV Ab and HCV RNA/antigen) and use of ART.
2. Recording specific clinical details to ensure female candidates are not women of CBP.
3. Physical examination (including height, weight and blood pressure).
4. Resting 12-lead ECG.
5. If results are not already available, routine blood will be taken for:
  - a. Full blood count (haemoglobin, haematocrit, white blood cell count (WBC) with differential and platelets).
  - b. Biochemistry tests (ALT, AST, alkaline phosphatase, total bilirubin, albumin, eGFR, creatinine kinase).
  - c. Urine Protein Creatinine Ratio (uPCR).
  - d. Lipids (total cholesterol, LDL, HDL, triglycerides).
  - e. T lymphocyte subsets (total lymphocytes, percent and/or absolute CD3/CD4/CD8).
  - f. Viral load measurements.
  - g. HbA1C (only if known diabetes mellitus).

Results of the clinical history and evaluations are to be entered on a case report form. Once clinic staff are satisfied that the participant is eligible for the study a completed screening CRF should be submitted to the RIVER Co-ordinating Centre for verification.

For Cohort I – Recently diagnosed, confirmation of enrolment will be sent to the site by email and also relayed over the telephone. Once this confirmation has been received the participant should be commenced on cART treatment as outlined in [Section 5.6](#). Eligibility for randomisation will be assessed at Week 22. For Cohort II – Previously diagnosed, eligibility for randomisation will be assessed at screening. Participants will not be randomised until all eligibility criteria have been met, see [Section 3.3.3](#), at which time the clinic staff will be informed which arm the participant has been allocated to.

